5.4 Efficacy Assessments

Study evaluations will take place in accordance with the flow charts in [Section 5.1](#). Baseline assessments should be performed within 28 days prior to the first dose utilizing CT or MRI. In addition to chest, abdomen, pelvis, and brain, all known sites of disease should be assessed at baseline. Subsequent assessments should include chest, abdomen, and pelvis, and all known sites

of disease and should use the same imaging method as was used at baseline. Subjects will be evaluated for tumor response beginning 6 weeks (± 1 week) from first dose and continuing every 6 weeks (± 1 week) for the first 24 weeks and every 12 weeks (± 1 week) thereafter, while on treatment or on treatment hold for any reason until disease progression and treatment discontinuation, whichever occurs later. Additionally, with the exception of crossover participants, tumor assessments will not be required upon initiation of subsequent anti-cancer therapy. Tumor assessments for ongoing study treatment decisions will be completed by the investigator using RECIST (Response Evaluation Criteria in Solid Tumors) 1.1 criteria ([Appendix 3](#)).

5.4.1 Primary Efficacy Assessment

The primary endpoint is objective response rate (ORR) in all assigned subjects as determined by the investigators. ORR is defined as the number of subjects with a best overall response (BOR) of complete response (CR) or partial response (PR) divided by the number of assigned subjects. The investigator-determined ORR will be further characterized by the investigator-determined duration of response (DOR) and the magnitude of reduction in tumor volume. ORR and DOR will be assessed by BICR in selected tumor types.

5.4.2 Best Overall Response

The best overall response is determined once all the data for the subject is known. It is defined as the best response designation, as determined by the investigator or BICR for selected tumor types, recorded between the date of first treatment and the date of objectively documented progression per RECIST1.1 or the date of subsequent therapy, whichever occurs first. For subjects without documented progression or subsequent therapy, all available response designations will contribute to the BOR assessment. The subject's best overall response assignment will depend on the findings of both target and non-target disease and will also take into consideration the appearance of new lesions.

Complete or partial responses may be claimed only if the criteria for each are met at a subsequent time point (minimum 4 weeks after criteria of objective response are first met). In this circumstance, the best overall response can be interpreted as in Table 5.4.2-1.

Table 5.4.2-1: Best overall response when confirmation of CR and PR required

Overall Response First Timepoint	Overall Response Subsequent Timepoint	Best Overall response
CR	CR	CR
CR	PR	SD, PD or PR ^a
CR	SD	SD provided minimum criteria for SD duration met, otherwise, PD
CR	PD	SD provided minimum criteria for SD duration met, otherwise, PD
CR	NE	SD provided minimum criteria for SD duration met,

Table 5.4.2-1: Best overall response when confirmation of CR and PR required

Overall Response First Timepoint	Overall Response Subsequent Timepoint	Best Overall response
		otherwise NE
PR	CR	PR
PR	PR	PR
PR	SD	SD
PR	PD	SD provided minimum criteria for SD duration met, otherwise, PD
PR	NE	SD provided minimum criteria for SD duration met, otherwise NE
NE	NE	NE

CR = complete response, PR = partial response, SD = stable disease, PD = progressive disease, and NE = inevaluable.

^a If a CR is truly met at first time point, then any disease seen at a subsequent time point, even disease meeting PR criteria relative to baseline, makes the disease PD at that point (since disease must have reappeared after CR). Best response would depend on whether minimum duration for SD was met. However, sometimes ‘CR’ may be claimed when subsequent scans suggest small lesions were likely still present and in fact the patient had PR, not CR at the first time point. Under these circumstances, the original CR should be changed to PR and the best response is PR.

For purposes of this study, the minimum scan time from baseline for determination of SD will be 6 weeks.

5.4.3 Duration of Objective Response

The duration of objective response is measured from the time measurement criteria are first met for confirmed CR/PR (whichever is first recorded) until the first date that progressive disease is objectively documented (taking as reference for progressive disease the smallest measurements recorded on study).

5.4.4 Immune related Response Criteria

Immune related response criteria using unidimensional measurements may be used to describe tumor shrinkage following RECIST 1.1 defined disease progression.⁸³ The methodology is the same as described above for RECIST 1.1 except for:

- New lesions do not automatically denote disease progression
- The measurement of longest diameter of new measurable lesions are included in the sum of the measurements of the original target lesions.

Best immune related responses, for subjects who have progression followed by tumor shrinkage are classified as irCR (disappearance of all lesions) or irPR ($\geq 30\%$ reduction from baseline).

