3.1.3 Staged Enrollment (Stage 1 and Stage 2)

3.1.3.1 Stage 1

This Stage is intended to assess the efficacy in 18 subjects per treatment arm per tumor type to determine whether enrollment should continue to Stage 2. For efficacy determination, each Arm within each tumor type will be assessed independently.

Arm N: The enrollment and treatment of 18 subjects to Arm N per tumor type can begin while the initial Dose Cohort for Arm N-I in this tumor type is still ongoing. The dose level in Arm N is 3 mg/kg nivolumab IV every two weeks (Q2W). This dose has been established in more than 700 subjects with various tumor types exposed to nivolumab monotherapy with a tolerable AE profile. Therefore no dose adjustments for Arm N are planned.

Arm N-I: Up to 18 subjects will be enrolled and treated in this arm per tumor type at the highest tolerated Dose Level determined during the Dose Escalating Safety Evaluation phase. The 3-9 subjects treated at the highest dose level confirmed for further investigation from the Dose Escalating Safety Evaluation phase will be counted as part of the 18 required subjects.

3.1.3.2 Criteria to proceed from Stage 1 to Stage 2

The decision to proceed from Stage 1 to Stage 2 will be made for each tumor and for each treatment arm independently and include ([Table 3.1.3.2-1](#)):

- 2 or more of 18 subjects in a given arm must have confirmed PR or CR before enrollment for that arm will be continued in Stage 2. The tolerability of the regimen will continue to be evaluated by the Sponsor with the investigators to ensure that it is acceptable for continued enrollment.
 - Subjects with initial PD per RECIST 1.1 who continue treatment in their initially assigned treatment arm beyond progression ([Section 4.5.7](#)) and subsequently reach confirmed immune related CR or PR (relative to initial tumor assessment) and including any new measurable lesions within the sum of all target lesions, will be considered as having an objective response for the purposes of meeting criteria for moving from Stage 1 to Stage 2. Although not standard RECIST 1.1, these immune related response criteria using unidimensional measurements account for the unusual immune related tumor response patterns reported for both ipilimumab and nivolumab.

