4.5.7 Treatment Beyond Disease Progression

As described in [Section 1.1.11](#) accumulating evidence indicates that subjects treated with immunotherapy may derive clinical benefit despite evidence of PD.⁸⁴

Subjects will be permitted to continue with treatment beyond initial RECIST 1.1 defined PD as long as they meet the following criteria:

- Investigator-assessed clinical benefit and
- Subject is tolerating study drug.

The assessment of clinical benefit should take into account whether the subject is clinically deteriorating and unlikely to receive further benefit from continued treatment. The following criteria need to be taken into consideration:

- Absence of clinical symptoms and signs (including worsening of laboratory values) indicating disease progression.
- No decline in ECOG performance status.
- Absence of rapid progression of disease or of progressive tumor at critical anatomical sites (eg, cord compression) requiring urgent alternative medical intervention.

Treatment with cobimetinib beyond progression as monotherapy or as part of the combination with nivolumab and ipilimumab is not permitted.

All decisions to continue treatment beyond progression must be discussed with the BMS Medical Monitor and documented in the study records.

Subjects must be re-consented in order to continue treatment.

Subjects should discontinue study therapy upon evidence of further progression, defined as an additional 10% or greater increase in tumor burden from time of initial progression (including all target lesions and new measurable lesions). Progression in non-target lesions should only be unequivocal as defined and described in [Appendix 3](#) compared to initial progression.

New lesions are considered measurable at the time of initial progression if the longest diameter is at least 10 mm (except for pathological lymph nodes, which must have a short axis of at least 15 mm).

For statistical analyses that include the investigator-assessed progression date, subjects who continue treatment beyond initial investigator-assessed, RECIST 1.1-defined progression will be considered to have investigator-assessed progressive disease at the time of the initial progression event. Subjects who have tumor shrinkage following RECIST-defined progression (ie, immune related response; [Section 5.4.4](#) will be also descriptively summarized separately since these immune responses may be used in determining Go to Stage 2.

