APPENDIX 3 RECIST 1.1

Changes in tumor measurements and tumor responses will be assessed by the investigator using the RECIST 1.1 (Response Evaluation Criteria in Solid Tumors) criteria. (Eisenhauer, et al 2009.)

Source: Eisenhauer et al New response evaluation criteria in solid tumours: Revised RECIST guideline (version 1.1), European Journal of Cancer, 2009, Vol. 45, p 228-247

1 **ASSESSMENT OF OVERALL TUMOR BURDEN AND MEASURABLE DISEASE**

To assess objective response or future progression, it is necessary to estimate the *overall tumor burden at baseline* and use this as a comparator for subsequent measurements. Measurable disease is defined by the presence of at least one measurable tumor lesion. When CT scans have slice thickness greater than 5 mm, the minimum size for a measurable lesion should be twice the slice thickness.

At baseline, tumor lesions/lymph nodes will be categorized measurable or non-measurable as follows:

1.1 **Measurable lesions**

Measurable lesions must be accurately measured in at least one dimension (longest diameter in the plane of the measurement to be recorded) with a minimum size of:

- 10 mm by CT/MRI scan - (CT/MRI scan slice thickness no greater than 5 mm)
- 10 mm caliper measurement by clinical exam (lesions which cannot be accurately measured with calipers should be recorded as non-measurable)
- 20 mm by chest x-ray
- *Malignant lymph nodes*: To be considered pathologically enlarged *and* measurable, a lymph node must be ≥ 15 mm in *short* axis when assessed by CT scan (CT scan slice thickness recommended to be no greater than 5 mm). At baseline and in follow-up, only the *short* axis will be measured and followed.

1.2 **Non-measurable lesions**

- All other lesions, including small lesions (longest diameter < 10 mm or pathological lymph nodes with ≥ 10 to < 15 mm short axis), as well as truly non-measurable lesions.
- Lesions considered truly non-measurable include: leptomeningeal disease, ascites, pleural or pericardial effusion, inflammatory breast disease, lymphangitic involvement of skin or lung, abdominal masses/abdominal organomegaly identified by physical exam that in not measurable by reproducible imaging techniques.

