2 BASELINE DOCUMENTATION OF 'TARGET' AND 'NON-TARGET' LESIONS

2.1 Target lesions

When more than one measurable lesion is present at baseline all lesions up to **a maximum of five lesions total (and a maximum of two lesions per organ) representative of all involved organs should be identified as target lesions** and will be recorded and measured at baseline.

Target lesions should be selected on the basis of their **size** (lesions with the longest diameter), be representative of all involved organs, and should lend themselves to **reproducible repeated measurements**.

A **sum of the diameters** (longest for non-nodal lesions, short axis for nodal lesions) for all target lesions will be calculated and reported as the **baseline sum diameters**. If lymph nodes are to be included in the sum, then as noted below, only the **short axis** is added into the sum. The baseline sum diameters will be used as reference to further characterize any objective tumor regression in the measurable dimension of the disease.

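### The immune-related sum adds new measurable lesions by longest diameter with no exception for lymph nodes, while the protocol otherwise measures and sums nodes by short axis; the literal rule can only under-call irPR, and the effect is small

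*Protocol*

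**What the plan says.** Section 5.4.4 defines the immune-related criteria by departure from RECIST: "The methodology is the same as described above for RECIST 1.1 except for" two listed items. The second is: "The measurement of longest diameter of new measurable lesions are included in the sum of the measurements of the original target lesions". Appendix 3, 4.3.3 carries the same two items, and both sections appear in Revised Protocol 07D and again in Revised Protocol 08. Neither mentions lymph nodes.

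Three other places bear on nodes:

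- Section 4.5.7 sets when a new lesion is measurable: a longest diameter of at least 10 mm, "except for pathological lymph nodes, which must have a short axis of at least 15 mm".
- Appendix 3, 1.1, on malignant nodes: "At baseline and in follow-up, only the *short* axis will be measured and followed".
- Appendix 3, 2.1, on the target sum: "longest for non-nodal lesions, short axis for nodal lesions) for all target lesions will be calculated".

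The result is used as follows. An irPR is a reduction of at least 30% from baseline (Section 5.4.4). Under Section 3.1.3.2, subjects who progress, stay on their assigned treatment and then reach a confirmed immune-related CR or PR "will be considered as having an objective response for the purposes of meeting criteria for moving from Stage 1 to Stage 2", where 2 of 18 are needed. Section 8.4.2.1 also summarises immune-related responses descriptively.

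**The concern.** A new node enters the set of measurable new lesions by its short axis and then enters the sum by its longest diameter. Nodes among the original targets stay in the same sum by short axis. The long axis of a node is also a dimension that Appendix 3 says is not followed, so the literal rule calls for a number the measuring rules do not collect. Two careful readers could classify the same scans differently.

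The error has one direction. Adding the long axis makes the follow-up sum at least as large as adding the short axis, and the baseline reference contains no new lesions. Some subjects with an irPR on a consistent sum would be recorded as having none. At stake are the immune-related response summary and, where an arm's Stage 1 decision relied on this sum, the count of responders.

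**Working it through.** **The plan's own figures.** Section 8.1 gives a two-stage design with 40 subjects, null ORR 10%, alternative 25%, a 5% Type I error target and 80% power. The gate is 2 or more of 18 (Section 3.1.3.2). The protocol does not print the final cut-off; 8 of 40 is inferred.

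P(reject) = sum over x = 2 to 18 of Bin(x; 18, p) × P(at least 8 - x responders among the other 22).

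This gives 4.05% at p = 0.10 and 80.7% at p = 0.25, so the stated figures reproduce. A cut-off of 7 gives a Type I error of 9.3%; a cut-off of 9 gives power of 69.4%.

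**When the axis changes the call.** Let B be the baseline sum, T the original targets at follow-up, S and L the short and long axes of a new node, with L ≥ S. The irPR is lost when

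T + S ≤ 0.70 B < T + L.

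The reverse, an irPR by long axis but not by short axis, would need L < S and cannot occur. irCR requires all lesions to disappear, so the choice of axis does not touch it.

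**Worked case.** Lesion sizes and axis ratios are assumptions; the protocol gives none. B = 60 mm, T = 25 mm, S = 15 mm, irPR threshold 0.70 × 60 = 42 mm.

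| New node counted by | Sum (mm) | Change from 60 mm | irPR |
|---|---|---|---|
| Short axis | 25 + 15 = 40 | -33% | yes |
| Long axis, ratio 1.3 | 25 + 19.5 = 44.5 | -26% | no |
| Long axis, ratio 1.5 | 25 + 22.5 = 47.5 | -21% | no |
| Long axis, ratio 2.0 | 25 + 30 = 55 | -8% | no |

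A second assumed case agrees. With B = 100, T = 55 and a new node of 15 × 25 mm, the sum is 70 (-30%, irPR) by short axis and 80 (-20%, none) by long axis.

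The call does not always change. With B = 100, T = 40 and a 15 × 25 mm node, the changes are -45% and -35%, an irPR either way. Only subjects near the 30% line are affected.

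**What it could do to the gate.** P(pass) = P(at least 2 of 18). The share of responses lost to the node rule is not in the documents, so 2%, 5% and 10% of all responses are assumed.

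| True ORR | No loss | 2% lost | 5% lost | 10% lost |
|---|---|---|---|---|
| 25% | 96.1% | 95.7% | 95.0% | 93.7% |
| 15% | 77.6% | 76.6% | 74.9% | 72.0% |

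The fall is about 0.4 to 2.4 points at 25% ORR and 1.0 to 5.6 points at 15%. Section 1.1.11 reports progression before response or stable disease in about 10% of subjects in an earlier nivolumab study. The category is therefore not empty, but that figure does not say how many had a new measurable node.

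**The case against.** The best defence is that the nodal rule is implied. Section 5.4.4 keeps RECIST methodology apart from two items, the purpose of the second is to bring new lesions into the sum, and longest diameter may be shorthand for a one-dimensional measure. That reading is possible, but the item is listed as an exception to RECIST, so on its face it displaces the nodal rule. The nodal exception written into Section 4.5.7 is absent here.

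The gate text is a stronger point. Section 3.1.3.2 does not say longest diameter. It places new measurable lesions within the sum of all target lesions, which Appendix 3, 2.1 builds with short axis for nodes. The gate can be run correctly from that section. If sites recorded only short axes, as Appendix 3 directs, the inflated sum may never have been computed.

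The reach is also limited:

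- Primary ORR stops at the initial RECIST progression (Section 8.3.1).
- The SCLC arms have already proceeded to Stage 2 (Section 3.1.4).
- The bladder, ovarian and additional pancreatic cohorts are one-stage.
- Under Section 3.1.3.2 an arm is closed only once its last subject has stopped treatment or reached the Week 48 assessment, so a near miss at one scan may be recovered at a later one.

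All of this limits the consequence. It does not remove the conflict between Section 5.4.4 and Appendix 3.

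**Conclusion.** The rule in Section 5.4.4 and Appendix 3, 4.3.3 is wrong as written: it combines two axes for nodes in one sum and contradicts the protocol's own measurement rules. The direction is certain, towards under-calling irPR. The size is not known and is probably small, since a subject must progress, have a new measurable node and then shrink to near the 30% threshold. The millimetre examples rest on assumed lesion sizes and axis ratios, and the gate figures on assumed loss rates.

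The descriptive immune-related summary is affected, as is the 2-of-18 count in any two-stage arm (gastric, original pancreatic, TNBC, SCLC) whose decision used this sum.

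A reader might infer more: that every new lesion is added, or that responding arms were stopped at Stage 1 because of this. The documents do not support either. The rule covers measurable new lesions only, the gate section does not itself call for longest diameter, and nothing shows that an arm failed, or still faces the gate, on this account.

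**What to change.** In Section 5.4.4 and Appendix 3, 4.3.3, in both Revised Protocol 07D and Revised Protocol 08, replace the second item with: 'the longest diameter of new measurable non-nodal lesions and the short axis of new measurable nodal lesions are included in the sum of the original target lesions'. This is one phrase in four places. It needs no new measurement, because the short axis is what Appendix 3 already has sites record.

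Section 4.5.7 also puts new measurable lesions into a tumor-burden increase used for treatment decisions, without saying which dimension of a node counts. How that burden is measured must be reconciled with Appendix 3; no rule is proposed here.

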5.5 Pharmacokinetic Assessments

Serum samples for nivolumab and ipilimumab PK and immunogenicity assessments will be collected for all subjects.

5.5.1 Pharmacokinetics: Collection and Processing

A detailed schedule of PK and immunogenicity evaluations is provided in Table 5.5.1-1, Table 5.5.1-2, Table 5.5.1-3, and Table 5.5.1-4. All timepoints are relative to the start of study drug administration. Pre-dose samples should be taken within 30 minutes prior to the start of the first infusion for the day (prior to the nivolumab dose). All on-treatment PK timepoints are intended to align with days on which study drug is administered, if dosing occurs on a different day due to minor scheduling shifts, the PK sampling should be adjusted accordingly. If PK and immunogenicity samples are drawn but study drug(s) is not administered on the same day, samples will be retained and analyzed as planned. There is no need to collect another sample when the dose is resumed. Further details of sample collection, processing, and shipment will be provided in the laboratory procedures manual.

Table 5.5.1-1: Pharmacokinetic & Immunogenicity Sampling Schedule - Arm N-I (Dose level 2 and 2b)

Study Day ^a	Event	Time (Relative to Start of Infusion) Hour: Min	Nivolumab PK Blood Sample	Nivolumab Immunogenicity Sample	Ipilimumab PK Blood Sample	Ipilimumab Immunogenicity Sample
D1 Week 1	Predose ^b	00:00	X	X	X	X
D1 Week 4	Predose	00:00	X	X	X	X
D1 Week 10	Predose	00:00	X	X	X	X
D1 Week 13	Predose	00:00	X	X		
D1 Week 25	Predose	00:00	X	X		
Day 1 of every 16th week until discontinuation of study treatment or completion of 2 years of study treatment	Predose	00:00	X	X		

^a If ipilimumab is discontinued and nivolumab continues, ipilimumab PK and Immunogenicity should be collected only for the next 2 timepoints (corresponding to ipilimumab sample collection) according to the PK table. If ipilimumab is discontinued, nivolumab will follow the same schedule as originally planned for that subject.

^b Predose samples for nivolumab and ipilimumab should both be collected prior to start of nivolumab infusion (preferably within 30 minutes). If the infusion is delayed and a pre-dose sample is already collected, there is no need to collect an additional pre-dose sample.

Table 5.5.1-2: Pharmacokinetic & Immunogenicity Sampling Schedule - Arm N

Study Day	Event	Time (Relative to Start of Infusion) Hour: Min	Nivolumab PK Blood Sample	Nivolumab Immunogenicity Sample	Ipilimumab PK Blood Sample	Ipilimumab Immunogenicity Sample
All Subjects in Arm N						
D1 Week 1	Predose	00:00	X	X		
D1 Week 3	Predose	00:00	X	X		
D1 Week 5	Predose	00:00	X	X		
D1 Week 13	Predose	00:00	X	X		
Day 1 of every 16th week until discontinuation of study treatment or completion of 2 years of study treatment	Predose	00:00	X	X		
Crossover Subjects Only (SCLC subjects from the expansion cohorts under or after Amendment 09 are excluded from this option)						
Crossover D1 Week 1	Predose ^a	00:00	X	X	X	X
Crossover D1 Week 4	Predose	00:00	X	X	X	X
Crossover D1 Week 10	Predose	00:00	X	X	X	X
Crossover D1 Week 13	Predose	00:00	X	X		
Crossover D1 Week 25	Predose	00:00	X	X		
Day 1 of every 16th week until discontinuation of study treatment or completion of 2 years of study treatment	Predose	00:00	X	X		

^a Predose samples for nivolumab and ipilimumab should both be collected prior to start of nivolumab infusion (preferably within 30 minutes). If the infusion is delayed and a pre-dose sample is already collected, there is no need to collect an additional pre-dose sample.

Table 5.5.1-3: Pharmacokinetic & Immunogenicity Sampling Schedule - Arm N-I (Dose level 2c)

Study Day ^a	Event	Time (Relative to Start of Infusion) Hour: Min	Nivolumab PK Blood Sample	Nivolumab Immunogenicity Sample	Ipilimumab PK Blood Sample	Ipilimumab Immunogenicity Sample
D1 Week 1	Predose ^b	00:00	X	X	X	X
D1 Week 7	Predose	00:00	X	X	X	X
D1 Week 19	Predose	00:00	X	X	X	X
After Week 19 Day 1, Day 1 of every 18th week until discontinuation of study treatment or completion of 2 years of study treatment	Predose	00:00	X	X	X	X

^a If ipilimumab is discontinued and nivolumab continues, ipilimumab PK and Immunogenicity should be collected only for the next 2 timepoints (corresponding to ipilimumab sample collection) according to the PK table.

^b Predose samples for nivolumab and ipilimumab should both be collected prior to start of nivolumab infusion (preferably within 30 minutes). If the infusion is delayed and a pre-dose sample is already collected, there is no need to collect an additional pre-dose sample.

Table 5.5.1-4: Pharmacokinetic & Immunogenicity Sampling Schedule for Arm N-I Combined with Cobimetinib (Dose level 2d) (Nivolumab and Ipilimumab Sample Collections)

Study Day (1 Cycle =6 Weeks)	Event	Time (Relative to Start of Infusion) Hour: Min	Nivolumab PK Blood Sample	Nivolumab Immunogenicity Sample	Ipilimumab PK Blood Sample	Ipilimumab Immunogenicity Sample
D1 Week 1 (D1 Cycle 1)	predose	00:00	X	X	X	X
D1 Week 3 (D15 Cycle 1)	predose	00:00	X	X	X	X
D1 Week 9 (D15 Cycle 2)	predose	00:00	X	X	X	X
D1 Week 15 (D15 Cycle 3)	predose	00:00	X	X	X	X
D1 Week 21 (D15 Cycle 4)	predose	00:00	X	X	X	X
Day 1 of every 24th (4 cycles) week after week 21 until discontinuation of study treatment or completion of 2 years of study treatment	predose	00:00	X	X	X	X

Note: Predose samples should be collected just prior to the start of infusion on the day the study drug is administered

